This project is a randomized, double-blind clinical trial that aims to supplement RA patients with vitamin E insufficiency with vitamin E for one month and evaluate the effect of vitamin E on clinical activity and inflammation in these patients. The risk is considered greater than minimal due to the use of randomized methods for assigning patients to vitamin E supplementation or placebo. This decision is based on the need to ensure the rigor and objectivity of the study. It is important to note that to date, no harmful interactions between vitamin E and standard RA treatment, which is based on DMARDs, glucocorticoids, and NSAIDs, have been reported, according to the PubMed, UpToDate, Drugs.com, and DrugBank platforms.

The suggested dose for supplementation is 800 mg/day is based on previous clinical trials that have demonstrated its potential anti-inflammatory effect and decreased RA activity. In addition, a study conducted by Dysken MW et al. in 2014 evaluated the safety of vitamin E for one year and no adverse effects were observed with supplementation. The supplement intended to be used is Tocofersolan (α -tocopherol), which has health registration with COFEPRIS (006V2002 SSA) and is manufactured by Gelpharma, SA de C. V (The researchers declare no conflict of interest). This supplement will be covered by the researchers. Supplementation of patients with vitamin E capsules will be from the same batch to ensure consistency, reproducibility, and validity of the results.

Based on the above, we are interested in determining whether supplementation with Vitamin E (α -tocopherol) for one month has effects on clinical activity and inflammation in patients with RA from Western Mexico.

4. Objectives

a. General objective

Evaluate the effects of supplementation with Vitamin E (α -tocopherol) in patients with RA, as well as its relationship to clinical activity and inflammation of the disease.

b. Specific objectives

1. To analyze the clinical characteristics and diet quality of patients with RA
2. To determine serum levels of autoantibodies in patients with RA
3. To quantify serum vitamin E levels before and after supplementation in both study groups (vitamin E and placebo)
4. To compare clinical activity before and after supplementation in both study groups
5. To quantify the serum concentration of the proinflammatory cytokines IL1 β , IL6 and TNF- α before and after supplementation in both study groups

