- Use of placebo: Participants will be informed that they could be taking either vitamin E or placebo. Both vitamin E and placebo will have similar excipients and will be masked by similar packaging.
- Double-blinding: To minimize bias in the study, it is important that both the researchers involved and the participants be blinded as to who is receiving the active treatment and who is receiving the placebo. Once the one-month supplementation period and data collection are

over, the study will be unblinded. A researcher independent of the project will maintain the double-blinding information.

- During the study, potential adverse events will be identified through scheduled consultations and spontaneous reports from participants, who will have access to a 24-hour communication channel. All events will be recorded in a standardized format (Naranjo Questionnaire and Adverse Event Recording Form), evaluated by the principal investigator or a safety committee, and classified according to their severity and relationship to treatment. Mild or moderate events will receive symptomatic treatment, while severe events will be reported to the appropriate authorities, with treatment suspension if necessary. Each affected participant will be monitored until the event is completely resolved, ensuring their safety and an appropriate response at all times.

b) Research venues

- Institute for Research in Biomedical Sciences (IICB) of the University Center for Health Sciences (CUCS)
- Clinical Analysis and Translational Research Laboratory (LACIT), at the University Center for Exact Sciences and Engineering (CUCEI)
- Rheumatology Service of the “Fray Antonio Alcalde” Civil Hospital in Guadalajara, Jalisco.

c) Study period

November 2024 to January 2027.

d) Inclusion criteria

Female sex, RA classification (ACR/EULAR 2010), early RA \leq 2 years, treatment with conventional synthetic DMARDs (methotrexate, hydroxychloroquine, leflunomide, sulfasalazine and their combinations) for more than one month, DAS28 \geq 3.2, vitamin E deficiency (<15 mg/day), no comorbidities: arterial hypertension, type 2 diabetes, dyslipidemias, severe interstitial lung disease, active or recent cancer (less than 5 years in remission), chronic infections (active tuberculosis, hepatitis B or C, HIV), age $>$ 18 years, voluntary participation and signing of informed consent.

e) Exclusion Criteria

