Liver and kidney diseases, overlap syndrome with other autoimmune diseases, coagulation disorders, pregnancy, consumption of supplements (iron, vitamin E and/or K), and medications such as aspirin, amlodipine, estrogens, glucocorticoids and medications used in the treatment of dyslipidemia in the last three months.

f) Elimination Criteria

Errors in supplement administration $\geq 20\%$: The treatment adherence form (Annex 14) will be used as the tool to be used, recording daily vitamin/placebo intake. Patients who fail to consume at least 80% of the total daily intake (48 capsules) will be eliminated from the study. Patients with adverse effects from the supplement (Annexes 15 and 16), pregnancy during the study, insufficient blood sample collection, and voluntary withdrawal of informed consent may be excluded.

g) Sample Size

The two-means statistical formula was used to calculate the sample size. To do this, the following data are required: Identify whether the hypothesis is unilateral or bilateral. Establish alpha and beta levels, and use them to determine the K value ($Z\alpha$ and $Z\beta$). The difference in measurements we would expect to find or want to be able to detect in our study ($\mu_1 - \mu_2$), the expected standard deviation for each group .

Calculations were performed using data from the 2001 clinical trial by Mona Helmy et al., resulting in a sample size of 19 patients plus a 20% increase to cover potential losses.

Data: Serum vitamin E levels: start: 0.64 mg/dL and end: 0.86 mg/dL

K value: 15.8 with a statistical power of 95%.

Standard deviation of vitamin E levels: start: 0.16 mg/dL and end: 0.18 mg/dL

Twenty-three patients were included in the control and intervention groups. Both groups had RA from the Rheumatology Service of the “Fray Antonio Alcalde” Civil Hospital in Guadalajara, Jalisco.

$$n = \frac{K(\sigma_1^2 + \sigma_2^2)}{(\mu_1 - \mu_2)^2}$$

Formula substitution:

$$n = \frac{15.8(0.16^2 + 0.18^2)}{(0.86 - 0.64)^2} = 18.93$$

$18.93 + 20\% \text{ in case of loss} = 22.7 = \mathbf{23 \text{ patients per group}}$

h) Variables

Independent variables

- Vitamin E

Dependent variables

- Inflammatory cytokines (IL-1 β , IL-6, and TNF- α). Antioxidant capacity (DPPH, ABTS, FRAP, and ORAC). Clinical course: DAS-28. Acute phase reactants: pCr and ESR. Autoantibodies: Anti-CCP and Rheumatoid factor.

Operationalization of variables			
Variable	Interrelationship	Nature	Indicator

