7.1 Clinical Evaluation

7.2 Medical record

The clinical evaluation will be carried out by a rheumatology specialist, who will perform a general physical examination and apply clinical evaluation indices such as:

DAS28 Clinical Activity Index : This index measures disease activity in patients with rheumatoid arthritis (RA). It is calculated using four variables: the red blood cell sedimentation rate (ESR), the number of swollen joints, the number of painful joints (evaluating a total of 28 joints), and a visual analog pain scale. A mathematical formula is then applied, providing a score from 0 to 10. A value greater than 5.1 indicates high disease activity, a value less than 3.2 indicates low activity, and a value less than 2.6 indicates disease remission.

SDAI (Simplified Disease Activity Index): The SDAI is a more simplified disease activity index compared to the DAS28. It is based on five parameters: the number of swollen joints, the number of tender joints, the visual analogue pain scale score, the ESR (or C-reactive protein), and the patient's global status. The total score can range from 0 to 86, and like the DAS28, values above 26.0 indicate high disease activity, while values below 3.3 reflect disease remission.

CDAI (Clinical Disease Activity Index): The CDAI is similar to the SDAI, but differs in that it does not include laboratory measurements, i.e., it does not use ESR or C-reactive protein. It is

calculated by adding the following parameters: number of swollen joints, number of tender joints, the score on the visual analog pain scale, and the patient's overall condition. The total score ranges from 0 to 76, and like the SDAI, values less than 10 indicate disease remission, while values greater than 22.0 indicate high disease activity.

HAQ-DI (Health Assessment Questionnaire Disability Index): The HAQ-DI is a tool used to measure the level of physical disability in patients with chronic diseases, such as rheumatoid arthritis. It assesses a patient's functional ability in eight categories: dressing, bathing, eating, getting out of bed, walking, reaching, bending, and performing activities of daily living. Each category is scored from 0 to 3 (with 0 being no difficulty and 3 being maximum difficulty), and the total score is obtained by adding the scores for each category and dividing by the total number of categories assessed. A higher score indicates greater functional disability.

7.3 24-hour reminder

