7.4 Clinical analysis

7.4.1 Blood sampling

The invitation to participate will be sent **before** the vitamin E intake assessment, as this is part of the clinical trial screening. Subsequently , a BD Vacutainer SST™ tube with a gold cap and a capacity to collect 5 ml of blood will be collected. It contains a polymer gel, silicone coating, and will be protected from sunlight or UV exposure to obtain serum. In addition, another BD Vacutainer tube with anticoagulant (EDTA) with a capacity to collect 4 ml of blood will be collected for ESR determination.

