7.4.4 Immunological analysis

To quantify serum levels of cytokines and autoantibodies in the study groups, serum will be obtained from a peripheral blood sample. The blood will be collected in a vacuum tube with a separating gel and centrifuged for 10 minutes at 3,000 rpm. Once the serum is separated, aliquots will be made into 0.6 mL microtubes, labeled, and stored at -80°C until the day of the assay.

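### Section 6 f) permits excluding a whole patient for a short blood sample, although some clinical-activity outcomes need no blood and others need only one of two tubes.

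*Protocol*

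**What the plan says.** Section 6 f) contains two kinds of rule. The adherence rule is mandatory: a patient below the capsule threshold "will be eliminated from the study". The second is permissive. Its grounds are adverse effects of the supplement, pregnancy, "insufficient blood sample collection, and voluntary withdrawal of informed consent may be excluded". It gives no minimum volume, does not say which tube or visit counts, and does not keep the patient in for outcomes she still has.

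Section 4 b), objective 4, is: "To compare clinical activity before and after supplementation in both study groups". Section 7.2 lists the indices for clinical activity and function. Of CDAI it says that it "differs in that it does not include laboratory measurements" and, more explicitly, that "it does not use ESR or C-reactive protein". HAQ-DI is a functional questionnaire. DAS28 is built from ESR, two joint counts and a pain scale.

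Section 7.4.1 describes two tubes: a gel tube for serum, and "another BD Vacutainer tube with anticoagulant (EDTA) with a capacity to collect 4 ml of blood will be collected for ESR determination". Section 7.4.3 uses 1 mL of the anticoagulated sample for ESR.

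**The concern.** A short sample is a shortfall in particular measurements, not in the patient. She may have taken her capsules, attended the visit and been examined. If she can be removed altogether, her joint counts, CDAI and HAQ-DI go with her, and so does DAS28 when only the serum tube was short. Clinical activity is one of the two effects named in the hypothesis (section 5), so these data are wanted.

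The exclusion is also discretionary, and at the one-month draw it falls after randomisation. Randomised patients should not leave the comparison at someone's discretion without need. Here there is no need, because the affected value can simply be recorded as missing.

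**Working it through.** **Step 1. What each result depends on**

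| Result | Needs | Serum tube short | EDTA tube short |
|---|---|---|---|
| CDAI (7.2) | joint counts, pain scale, global status | available | available |
| HAQ-DI (7.2) | questionnaire | available | available |
| DAS28 (7.2) | joint counts, pain scale, ESR | available | lost |
| ESR (7.4.1, 7.4.3) | EDTA tube | available | lost |
| Vitamin E, CRP, RF, anti-CCP, cytokines (7.4.2 to 7.4.7) | serum | at risk | available |
| DPPH, ABTS, FRAP, ORAC (7.4.8) | specimen not named | unclear | unclear |

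SDAI is left out because section 7.2 allows either ESR or CRP in it. For antioxidant capacity, section 6 i) lists whole blood, plasma and serum without assigning them to assays, so no claim is made. No single-tube shortfall removes all of a patient's outcomes, and even losing both tubes leaves CDAI and HAQ-DI.

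**Step 2. The plan's own sample size (6 g)**

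Inputs: K = 15.8; SDs 0.16 and 0.18 mg/dL; means 0.64 and 0.86 mg/dL.

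n = 15.8 × (0.16² + 0.18²) / (0.86 − 0.64)² = 15.8 × 0.0580 / 0.0484 = 18.93, rounded to 19.

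18.93 × 1.2 = 22.7, rounded to 23 per group. The stated figure reproduces. The margin for all losses is 23 − 19 = 4 per group, shared with non-adherence, adverse effects, pregnancy and withdrawal.

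**Step 3. Cost of excluding whole patients**

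One exclusion: 1/23 = 4.3% of an arm, from every outcome.

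Interval width is proportional to 1/√n at equal arm sizes and a fixed SD. The numbers excluded are assumptions:

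- two per arm: √(23/21) − 1 = 4.7% wider;
- three per arm: √(23/20) − 1 = 7.2% wider;
- all four per arm: √(23/19) − 1 = 10.0% wider.

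**Step 4. Outer illustration**

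Assume two-sided alpha 0.05, a normal approximation, and an outcome that needs no blood. The detectable difference at 80% power is (1.960 + 0.842) × √(2/n) in SD units: 0.83 at n = 23 and 0.91 at n = 19. Power for a 0.8 SD difference is 77% at n = 23 and 69% at n = 19. This bounds the case in which the whole margin is used up. It is not a forecast for short samples, for which the protocol gives no rate.

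**The case against.** The strongest reply has five parts.

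- **Listed outcomes.** CDAI and HAQ-DI are not among the dependent variables in 6 h), and every variable listed there needs blood, DAS28 included through ESR. This is true and limits the reach of the point. But section 7.2 has both instruments applied, objective 4 concerns clinical activity, and DAS28 is listed and survives a short serum tube.
- **Rationale.** Serum vitamin E is the independent variable and the basis of the sample size, so requiring a usable sample has some logic. That justifies leaving her out of analyses that use serum vitamin E. It does not justify leaving her out of the between-arm comparison of clinical activity.
- **The wording is permissive and the SAP is not shown.** Both are true. But permission to exclude the patient is written into the protocol, and a SAP that always kept her would depart from 6 f). Permissive wording also makes the exclusion discretionary, which is no safeguard.
- **The loss allowance.** The 20% covers lost numbers. It gives no reason to discard outcomes that were measured.
- **Size.** The effect is small and the counts are assumed. This stands.

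Two stronger readings are tempting and are not supported. A reader might infer that exclusions could be decided with the arms known, because serum is "labeled, and stored at -80°C until the day of the assay" and a shortage could surface late. But 6 f) speaks of collection, most naturally a failed draw at the visit, and section 6 a) says that once the supplementation month and data collection are "over, the study will be unblinded". Whether the assays count as data collection is not stated, so exclusion after unblinding is speculation. A reader might also infer that DAS28 would usually be salvageable. The protocol does not say how often samples fall short or which tube fails, and a difficult draw could affect both.

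**Conclusion.** The point holds as a modest design flaw. Section 6 f) allows a whole patient to be dropped for a shortfall that, on the protocol's own description, affects only some of her results. The consequences are an avoidable loss of precision on clinical activity and a needless discretionary exclusion, which is post-randomisation at the one-month draw.

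The loss is 4.3% of an arm per exclusion. Intervals would be about 4.7% or 7.2% wider if two or three per arm were excluded; those counts are assumed, and the true number may be smaller. The conclusion rests on sections 7.2, 7.4.1 and 7.4.3 as written and does not depend on the specimen used for antioxidant capacity. No bias between arms has been shown. The stated sample size is not affected.

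**What to change.** Delete the insufficient-sample ground from 6 f). Add a sentence to this effect: a short or missing blood sample makes only the results that depend on that sample missing; the patient remains in the study and in every comparison for which she has data (DAS28 if ESR is available, CDAI and HAQ-DI if assessed). State also that the reason for each missing assay is logged before the treatment code is opened.

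This changes no visit, assay or treatment. The cost is a short text amendment, plus tables that report the number analysed for each outcome, since those numbers will differ slightly.

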7.1 Clinical Evaluation

7.2 Medical record

The clinical evaluation will be carried out by a rheumatology specialist, who will perform a general physical examination and apply clinical evaluation indices such as:

DAS28 Clinical Activity Index : This index measures disease activity in patients with rheumatoid arthritis (RA). It is calculated using four variables: the red blood cell sedimentation rate (ESR), the number of swollen joints, the number of painful joints (evaluating a total of 28 joints), and a visual analog pain scale. A mathematical formula is then applied, providing a score from 0 to 10. A value greater than 5.1 indicates high disease activity, a value less than 3.2 indicates low activity, and a value less than 2.6 indicates disease remission.

SDAI (Simplified Disease Activity Index): The SDAI is a more simplified disease activity index compared to the DAS28. It is based on five parameters: the number of swollen joints, the number of tender joints, the visual analogue pain scale score, the ESR (or C-reactive protein), and the patient's global status. The total score can range from 0 to 86, and like the DAS28, values above 26.0 indicate high disease activity, while values below 3.3 reflect disease remission.

CDAI (Clinical Disease Activity Index): The CDAI is similar to the SDAI, but differs in that it does not include laboratory measurements, i.e., it does not use ESR or C-reactive protein. It is

calculated by adding the following parameters: number of swollen joints, number of tender joints, the score on the visual analog pain scale, and the patient's overall condition. The total score ranges from 0 to 76, and like the SDAI, values less than 10 indicate disease remission, while values greater than 22.0 indicate high disease activity.

HAQ-DI (Health Assessment Questionnaire Disability Index): The HAQ-DI is a tool used to measure the level of physical disability in patients with chronic diseases, such as rheumatoid arthritis. It assesses a patient's functional ability in eight categories: dressing, bathing, eating, getting out of bed, walking, reaching, bending, and performing activities of daily living. Each category is scored from 0 to 3 (with 0 being no difficulty and 3 being maximum difficulty), and the total score is obtained by adding the scores for each category and dividing by the total number of categories assessed. A higher score indicates greater functional disability.

7.3 24-hour reminder

It will be performed by the nutritionist, who will ask about the foods consumed the previous day and thus assess the quality of the diet and vitamin E intake.

The 24-Hour Recall (Appendix 17) is a subjective, retrospective method conducted through an in-person or telephone interview. This method relies on accurate recall, describing and quantifying the foods consumed the day before the visit. All food intake, including time and place, must be described in detail. To ensure greater reliability of the survey results, questions about food consumption will be asked on three days (Tuesday, Thursday, and Saturday). The information provided is then analyzed using specialized software (Nutritionist Pro™) to count calories, macronutrients, and micronutrients.

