Vitamin E	Independent	Quantitative	$\mu\text{g}/\text{dl}$
Proinflammatory cytokines (IL-1 β , IL-6 and TNF- α)	Dependent	Quantitative	pg/ml
VSG	Dependent	Quantitative	mm/hr
C-reactive protein	Dependent	Quantitative	mg/l
Anti-CCP	Dependent	Quantitative	UR/ml
Rheumatoid factor	Dependent	Quantitative	IU/ml
Antioxidant capacity (DPPH, ABTS, FRAP and ORAC)	Dependent	Quantitative	$\mu\text{mol}/\text{L}$
DAS28	Dependent	Quantitative	Remission: < 2.6 Low activity: $\geq 2.6 < 3.2$ Moderate: $\geq 3.2 < 5.1$ High: ≥ 5.1

i) Biosecurity considerations

In this study, the guidelines established in the Mexican Official Standards, NOM-052-SEMARNAT-2005, will be applied. NOM-054-SEMARNAT-1993, NOM-003-SSA2-1993 and NOM-087-ECOL-SSA1-2002 which refer to the classification, handling, storage and disposal of hazardous waste, chemical reagents and biological-infectious, in order to guarantee the protection of people who are in contact with them and the environment (annex 1 and 2).

The biological material to be used will be whole blood, plasma, and serum. These biological samples will be obtained from RA patients in an in vivo experimental model (clinical trial). Blood sampling will be performed by trained personnel. Sharps will be disposed of in rigid red

polypropylene containers, based on the Classification of Establishments Generating Hazardous Biological-Infectious Waste in NOM-087-ECOL-SSA1-2002. This procedure will be performed by a PhD student and a Rheumatology resident in the Rheumatology Service of the Fray Antonio Alcalde Civil Hospital.

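### Section 7.2 defines DAS28 with a pain scale as its fourth variable, so the entry limit and the activity categories are applied to a modified index

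*Protocol*

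**What the plan says.** Section 7.2 describes DAS28 as follows: "It is calculated using four variables: the red blood cell sedimentation rate (ESR), the number of swollen joints", then "the number of painful joints (evaluating a total of 28 joints), and a visual analog pain scale". No global or general-health rating by the patient is among the four variables. The scoring step is mentioned but not shown: "A mathematical formula is then applied, providing a score from 0 to 10". The limits follow: "A value greater than 5.1 indicates high disease activity, a value less than 3.2 indicates low activity", with remission below 2.6.

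The score is used in three places:

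- Section 6 d), Inclusion criteria, sets the entry limit: "DAS28 \geq 3.2, vitamin E deficiency".
- Section 6 h), Variables, names it among the dependent variables: "Clinical course: DAS-28".
- The operationalization table in section 6 h) grades it by the same limits, beginning "Remission: < 2.6 Low activity".

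In section 7.2 the CDAI is said to add to the joint counts "the score on the visual analog pain scale, and the patient's overall condition". The SDAI description likewise gives the pain scale and the patient's global status as separate items. Nothing elsewhere in the protocol redefines the fourth DAS28 variable.

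**The concern.** DAS28 is a named index with fixed components, and its category limits have meaning only for the score built from those components. In the standard ESR version the fourth component is the patient's global (general-health) rating. Section 7.2 puts pain there and keeps the limits.

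The protocol's own text argues against reading this as a synonym, because SDAI and CDAI list pain and the global rating side by side as different things. A site that follows section 7.2 literally would put the pain mark into the formula.

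Two uses of the score are affected. One is who enters, since 3.2 is an inclusion limit. The other is how disease activity is scored and graded before and after supplementation, which is specific objective 4.

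**Working it through.** **Does any figure in the protocol depend on DAS28?** The only computed figure is the sample size, and it uses serum vitamin E. With K = 15.8, standard deviations 0.16 and 0.18, and means 0.64 and 0.86 mg/dL (section 6 g):

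- n = 15.8 × (0.0256 + 0.0324) / 0.22² = 15.8 × 0.0580 / 0.0484 = 18.93
- 18.93 × 1.20 = 22.7, rounded up to 23 per group

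This reproduces the stated figure, and the DAS28 definition does not enter it.

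**Components as listed in section 7.2**

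| Index | Joint counts | Laboratory | Pain scale | Patient global | Examiner global |
|---|---|---|---|---|---|
| DAS28 | swollen, painful (28) | ESR | yes | no | no |
| SDAI | swollen, tender | ESR or CRP | yes | yes | no |
| CDAI | swollen, tender | none | yes | yes | no |

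The SDAI and CDAI rows show that the protocol treats pain and patient global as distinct. The DAS28 row shows which of the two it puts in the fourth place.

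**Limits applied to the score.** Section 7.2 and the table in section 6 h) use the same values (2.6, 3.2, 5.1) and differ only at exactly 5.1. Section 6 d) uses 3.2 for entry.

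**Size of the shift.** The protocol gives no weights. Assume the conventional DAS28-ESR form, with the rating in mm on a 100 mm scale:

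score = 0.56 √(tender) + 0.28 √(swollen) + 0.70 ln(ESR) + 0.014 × rating

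Replacing global by pain changes the score by 0.014 × (pain − global):

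| Pain minus global (mm) | Shift in score |
|---|---|
| 5 | 0.07 |
| 10 | 0.14 |
| 20 | 0.28 |
| 30 | 0.42 |

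A negative gap gives the same shift downwards. The gap is not in the protocol, so these rows are a range and not an estimate.

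**Illustration at the entry limit.** Take 2 tender joints, 1 swollen joint and ESR 15:

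- Without the rating: 0.56 × 1.414 + 0.28 × 1 + 0.70 × 2.708 = 0.79 + 0.28 + 1.90 = 2.97
- Rating of 10 mm: 2.97 + 0.14 = 3.11, not eligible
- Rating of 20 mm: 2.97 + 0.28 = 3.25, eligible

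A patient who marks 10 mm on one scale and 20 mm on the other is in or out according to which scale is used. If the gap is at most 30 mm, a patient whose score lies more than 0.42 from every limit cannot change class.

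**The case against.** The strongest reply is that the case leans on a definition from outside the protocol. Section 7.2 gives neither a formula nor a reference for DAS28. Listing pain and global separately under SDAI and CDAI proves that the protocol distinguishes them, but not which one DAS28 requires. The text is a short description for a rheumatology specialist, who may well record a global rating in practice. It is loose elsewhere too, for instance in allowing ESR in the SDAI.

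Much of this stands. The weight of 0.014 and the link between the limits and the global rating are assumptions from the standard index, and practice may be better than the text. But the protocol invokes the index by name and applies its limits, and it states the fourth variable explicitly. What is written is a scoring rule that departs from the index named.

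A reader might infer more than the documents support:

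- *That the treatment comparison is biased.* Both randomised groups are scored in the same way, so the substitution alone does not bias the contrast.
- *That pain in all three indices makes their agreement partly built in.* Section 6 h) lists only DAS28 as an outcome, and the protocol does not rely on agreement. The indices share joint counts under any definition, and after correction would still share the patient's global rating.
- *That results could not be set against the DAS28 reduction cited in Table 2.* That table gives no DAS28 value. The cited trial used 400 mg/day for 3 months, and no numerical comparison is planned.
- *That the same substitution occurs in SDAI and CDAI.* There the patient's global is present, and what is absent beside it is an examiner's global. That is a different discrepancy.

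**Conclusion.** The point holds in a limited form. As written, section 7.2 scores entry and the clinical-course variable on a modified DAS28 while applying the limits of the standard one. Under the conventional weight, a difference of 10 to 30 mm between pain and global moves the score by 0.14 to 0.42 in either direction. That can change eligibility or category for patients near 2.6, 3.2 or 5.1, and for no others.

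It does not by itself bias the between-group comparison and does not alter the 23 per group. The conclusion rests on two assumptions: the standard definition of DAS28-ESR, and a gap whose size and sign the protocol does not give. It is worth correcting because the score governs entry and is the listed clinical outcome, and because the correction is cheap.

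**What to change.** In section 7.2:

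1. Name the patient's global rating as the fourth DAS28 component, with its scale and units.
2. Write out the DAS28-ESR formula.
3. State that this one formula is used at screening, baseline and one month.
4. Record the pain scale as a separate item outside DAS28.

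As a secondary point, check the SDAI and CDAI component lists against the definitions of those indices, since both list pain and neither lists an examiner's global rating.

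The cost is a form and wording change. The patient's global rating is already listed for SDAI and CDAI, so no new patient-reported measure should be needed, although the protocol shows no collection form to confirm this. If any patients were scored before the change, their DAS28 can be recomputed only where the global rating was recorded. That favours making the change early.

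### Section 7.2 lets the SDAI laboratory item be ESR or CRP with no unit, although the protocol's own score ranges leave that item only 10 points

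*Protocol*

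**What the plan says.** Section 7.2 names the indices that the rheumatologist applies.

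- **SDAI.** It is said to rest on five parameters. Two are joint counts and one is a pain scale; the text then names "the ESR (or C-reactive protein), and the patient's global status. The total score can range from 0 to 86". On the cut-offs it says that "values above 26.0 indicate high disease activity, while values below 3.3 reflect disease remission". No formula, weight or unit is given.
- **CDAI.** Set against the SDAI, this is presented as an index that "differs in that it does not include laboratory measurements, i.e., it does not use ESR or C-reactive protein". The section describes it as a plain sum of the four clinical items and gives its range in these words: "The total score ranges from 0 to 76".

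The units come from elsewhere. The operationalization table in section 6 h) gives ESR (listed there as VSG) in mm/hr, and for CRP it reads "C-reactive protein Dependent Quantitative mg/l". That table has no SDAI row. Both tests are run on study samples under section 7.4.3.

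**The concern.** The two ranges, read together, fix how much the laboratory item may contribute. The permitted inputs do not respect that limit in the units the protocol uses. The text also treats ESR and CRP as alternatives under the same range and cut-offs, so one patient can receive different totals depending on which result is entered.

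What is at stake is the meaning of any SDAI result reported under specific objective 4 (clinical activity before and after supplementation). If ESR in mm/hr were simply added, a change of 10 mm/hr would weigh as much as ten swollen joints. The SDAI would then lean heavily on a marker that section 6 h) already lists as a dependent variable of its own.

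**Working it through.** **Inputs from the protocol.** SDAI range 0 to 86, CDAI range 0 to 76, SDAI cut-offs 26.0 and 3.3 (section 7.2); 28 joints assessed (section 7.2, stated for the DAS28); ESR in mm/hr and CRP in mg/l (section 6 h).

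**Assumptions.** The pain and global scales run 0 to 10, the joint counts use the same 28 joints, and the patient's global status in the SDAI is the same item as the overall condition in the CDAI.

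**Step 1: reproduce the stated ranges.** CDAI maximum = 28 + 28 + 10 + 10 = 76, as stated. The SDAI adds only the laboratory item, so its room is 86 - 76 = 10. The stated 86 is reproduced only if that item cannot exceed 10.

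**Step 2: maximum total if the laboratory value is added unscaled (76 + value).**

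| Laboratory value (mm/hr or mg/l) | Maximum total |
|---|---|
| 10 | 86 |
| 20 | 96 |
| 30 | 106 |
| 60 | 136 |
| 100 | 176 |

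**Step 3: cut-offs under unscaled addition.** A value of 27 with no swollen or tender joints and zero on both scales gives 0 + 27 = 27, above 26.0. A value of 3.3 or more leaves no total below 3.3.

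**Step 4: one illustrative patient (assumed values).** Three swollen joints, four tender joints, pain 4 and global 4 give 3 + 4 + 4 + 4 = 15. Take ESR 30 mm/hr and CRP 12 mg/l.

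- With ESR: 15 + 30 = 45, high.
- With CRP in mg/l: 15 + 12 = 27, high by one point. A CRP of 11 would give 26, which is not above the cut-off.
- With CRP in mg/l divided by 10: 15 + 1.2 = 16.2, not high.

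**Step 5: how many patients could change category.** The protocol gives no distribution of ESR, CRP or joint counts, so this was simulated. The clinical sum was gamma with coefficient of variation 0.5 and mean 10 to 40, capped at 76. The laboratory value was an independent lognormal with log-SD 0.7 and median 5 to 40. Categories (below 3.3, 3.3 to 26, above 26) were compared between the unscaled value and the value divided by 10, capped at 10.

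- Lowest share: 10% (clinical mean 40, laboratory median 5).
- Middle of the grid: 53% (clinical mean 20, laboratory median 20).
- Highest share: 86% (clinical mean 10, laboratory median 40).
- In the scenarios run, the share passed 50% only with a clinical mean of 20 or less and a laboratory median of 20 or more.

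**Step 6: a scale that fits.** CRP in mg/l divided by 10 contributes 0 to 10 for values from 0 to 100 mg/l, and 76 + 10 = 86.

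**The case against.** The strongest reply is that the protocol never says unscaled values are added. Section 7.2 gives no SDAI formula; only the CDAI is described as a sum. The mm/hr and mg/l units describe ESR and CRP as variables in their own right, in a table that omits the SDAI. A rheumatologist may well use a standard calculator that scales the item correctly. This stands: unscaled addition is an inference, although these are the only units the reader is given. It does not rescue the ESR alternative, because two different quantities still share one range and one pair of cut-offs.

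A reader might also infer that most patients would be misclassified. The documents do not support that. They give no distribution of the inputs, the simulated range is wide, and a patient whose clinical items already sum above 26 does not change category. Nor do they say how often ESR or CRP exceeds 10 in these patients.

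Nor does the protocol by itself dictate a particular analyte or divisor. The ranges imply a term of at most 10 and nothing more.

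Finally, the reach is limited. Section 6 h) lists DAS28 as the clinical-activity variable, section 6 d) uses DAS28 for entry, and section 6 g) sizes the trial on serum vitamin E. The SDAI appears in none of them. This stands too, and it confines the point to SDAI results.

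**Conclusion.** Wrong as written. The definition permits laboratory inputs that the stated range cannot hold in the protocol's own units, and it makes two different quantities interchangeable under one set of cut-offs. The 10-point limit follows directly from the two stated ranges once the CDAI is read as the SDAI without its laboratory item. The consequences for the cut-offs hold on condition that values are added in mm/hr or mg/l.

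Some patients can be misclassified. How many cannot be said from the protocol: the range of about 10% to 86% rests wholly on assumed distributions and should not be read as an estimate for this trial. Eligibility, sample size and the DAS28 comparison are untouched.

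**What to change.** In section 7.2, remove the ESR alternative from the SDAI. Define the laboratory item as one analyte, in one stated unit and scale, consistent with the 0 to 86 range and the 26.0 and 3.3 cut-offs. CRP in mg/l divided by 10 is one definition that fits, for values up to 100 mg/l; if it is adopted, state how higher values are handled. Write the SDAI out as a formula, and require the same definition for all patients at baseline and at one month.

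The cost is one sentence in the protocol and one conversion in the database. CRP is already measured under section 7.4.3, so no further sample or visit is needed. Any SDAI already calculated can be recomputed if its components were stored.
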